### **9.2 SETTING**

#### **9.2.1 Study sites**

This is a National multicenter study that will enroll patients in 10-12 sites, academic hospitals and reference centers. All included sites are reference centers for IPF. Furthermore, sites both in Athens and rest of Greece are included in the study so as patients enrolled will constitute a representative population of IPF patients in Greece.

## **9.2.2 Study population**

Newly diagnosed IPF patients initiating treatment with nintedanib according to their physician's clinical decision will be enrolled in this study. In details, patients will be eligible to enroll in the study if they fulfil all the inclusion criteria and none of the exclusion criteria:

### **Inclusion criteria**

- Patients  $\geq$ 40 years of age.
- Patients that have signed Informed Consent Form.
- Treatment naive patients with an initial IPF diagnosis no more than 3 months prior to enrolment according to 2011 ATS/ERS/JRS/ALAT guidelines who are initiating treatment with nintedanib (as monotherapy for IPF), the latest on the enrollment day or have initiated treatment with nintedanib (as monotherapy for IPF) within the past 7 days prior to enrolment.
- Patients for whom the decision to prescribe therapy with nintedanib according to the locally approved product's Summary of Product Characteristics (SmPC) has already been taken prior to their enrolment in the study and is clearly separated from the physician's decision to include the patient in the current study.
- Patients that are able to read, understand and complete the study specific questionnaires.

### **Exclusion criteria**

- Treatment with nintedanib for more than 7 days prior to study enrolment.
- Patients receiving a combination therapy of nintedanib & pirfenidone for IPF.
- Patients that meet any of the contraindications to the administration of the study drug nintedanib according to the approved SmPC.
- Prior treatment with pirfenidone or other treatment for IPF.
- Participation in an interventional study.
- Patients currently receive treatment with any investigational drug/device/intervention or have received any investigational product within 1 month or 5 half-lives of the investigational agent (whichever is longer) before the initiation of therapy with nintedanib.

According to study design, enrolled patients will constitute a representative population of newly diagnosed IPF patients in Greece. Recruitment will last for 36 months and patients will be followed over a period of 52 weeks post enrollment. A baseline visit and estimated 4 follow up visits will be performed during the follow-up period according to clinical practice. Patients will be included in a consecutive manner at each site between February 2019 and February 2022 in order to avoid selection bias.

A subject screening log should be kept at the site, recording basic information (e.g. initials, gender, date of birth, reason for not enrolling the patient etc.) on all patients who were invited to participate in the study, with the information on the eligibility (or reasons for non-eligibility) and date of signed informed consent. In the case of refusal, reasons for refusal should be given. In addition, a log of all patients included into the study (i.e. having given informed consent) will be maintained in the study file at the study site.

#### **9.2.3      Study visits**

The study is scheduled to run for 4 years in total, i.e. 3 years of recruitment and 1 year of follow-up. During the follow up period, data will be collected on 4 standard clinical visits which usually are scheduled around: 3-months ( $\pm$  1 month), 6-months ( $\pm$  1 month), 9-months ( $\pm$  1 month), 12-months ( $\pm$  1 month) until the end of participation in the study. Patients that permanently discontinue nintedanib treatment for any reason (e.g. due to AE, consent withdrawal, lost to Follow-up) prior to the follow up period completion, will no longer be followed-up for the study and the visit that nintedanib discontinuation is recorded will be considered as their end of study visit.

#### **9.2.4      Patient discontinuation**

Patients will be followed up for a 52-weeks follow-up period according to clinical practice and will be considered that completed the study upon completion of the last FU data collection at week 52. Patients that withdraw from the study prior to the follow up period completion, for any reason (consent withdrawal, lost to follow up) will no longer be followed-up for the study and the visit that discontinuation is recorded will be considered as their final, end of study visit.

In case of patient's permanently treatment discontinuation for any reason (e.g. due to AE, physician's decision), patients will be considered as prematurely/early discontinued and will not be further followed up in the scope of the study. The visit that discontinuation is recorded will be considered as their final, end of study visit.

Patients that temporarily interrupt treatment with nintedanib, up to 28 days, will continue follow up activities according to the study plan and will not be discontinued from the study. In case of dose reduction during the course of the study and re-start, patients will continue their participation and information on treatment administration will continue to be captured (dose reduction, treatment re-start and dose).

Patients reserve the right to discontinue their participation in the study at any time during its conduct and for any reason, without having to justify their decision and with no impact on their future medical care and therapy.

Consent withdrawal means that a patient does not want or is unable to further continue participating in the study.

The reasons for patient's discontinuation may include the following:

- patient's withdrawal of informed consent;
- discontinuation of study treatment (nintedanib) due to any reason;
- the patient meets an exclusion criterion (either newly developed or not previously recognized) that precludes further study participation;
- enrollment or planned participation in any clinical trial, at any time during the study observation period, in which the patient has been or will be exposed to an investigational product (pharmaceutical agent or device) or intervention;
- investigator's/physician's decision;
- significant protocol deviation/violation.

Patients, who withdraw from the study, should be asked about the reason(s) for discontinuation and the occurrence of any adverse events, and, if applicable, they shall be examined and evaluated by the investigator as per the procedures defined in the Final / Discontinuation Visit.

Furthermore, investigators will have the right to withdraw any patient from the study, if according to their clinical judgment this decision is considered to be in the patient's best interest.

If a patient withdraws or is removed from the study for any reason, the reason for and date of the discontinuation as well as the date of the last dose of study medication should be recorded in the appropriate section of the electronic Case Report Form (eCRF).

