## **9. RESEARCH METHODS**

### **9.1 STUDY DESIGN**

This is a National, multi-center, non-interventional, prospective cohort study aiming to enroll 240 IPF patients receiving treatment with nintedanib in a consecutive manner from 10-12 reference centers across Greece, representative of the entire Greek population. Recruitment will last for 36 months and patients will be followed over a period of 52 weeks. Only consecutive patients with newly diagnosed IPF patients (initial IPF diagnosis no more than 3 months prior to enrolment) according to 2011 ATS/ERS/JRS/ALAT guidelines who are initiating treatment with nintedanib will be enrolled to restrict selection bias. A baseline visit and estimated 4 follow up visits will be performed during the follow-up period according to clinical practice. In the context of this study, participating physicians shall follow each enrolled patient for a planned observation period of 12 months, starting from the date of baseline visit and ending at the earliest of treatment discontinuation, withdrawal of consent, physician's decision to withdraw the patient, 12-month observation period completion, death or any other discontinuation criterion is met.

Patients that permanently discontinue nintedanib treatment for any reason (e.g. due to AE, consent withdrawal, lost to Follow-up) prior to the follow up period completion, will no longer be followed-up for the study and the visit that nintedanib discontinuation is recorded will be considered as their end of study visit.

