### **9.3.2 Endpoints**

#### **9.3.2.1 Primary endpoint**

The primary endpoint of the study is:

- The mean change from baseline in HRQoL (with reference to SGRQ score, both total score and score in each of the SGRQ domains) of patients under treatment with nintedanib, as assessed by the changes in SGRQ score at time-points of 3, 6, 9 and 12 months over the 52 weeks follow-up period.

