6-minute walk distance			
Treatment with Nintedanib (start date, stop date, restart date in case of temporary discontinuation and daily dose)	x	x	x
Long-Term-Oxygen-Therapy (liquid and/or concentrate)	x	x	x
Questionnaires			
SGRQ	x	x	x
mMRC	x	x	x

Cough - VAS	X	X	X
GAD-7	X	X	X
SMAQ		X	X
Survival status		X	X
Reason for treatment discontinuation			X

For abbreviations, please refer to glossary.

\*3-months ( $\pm$  1 month), 6-months ( $\pm$  1 month), 9-months ( $\pm$  1 month),

\*\* Final visit is designated as either the 12 months ( $\pm$  1 month) follow up visit for all patients that remain on study until that time-point or the visit performed at the time of a patient's discontinuation or withdrawal from the study.

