### 7.4 PRIMARY ENDPOINT(S)

#### 7.4.1 Primary analysis of the primary endpoint(s)

The SGRQ Total score and the corresponding sub domains will be calculated; it summarizes the impact of the disease on the overall health status. Scores are expressed as a percentage of

overall impairment where 100 represents worst possible health status and 0 indicates best possible health status.

The primary endpoint of SGRQ Total score and the corresponding sub domains will be summarized descriptively as continuous variables at each study visit in the TS population.

The SGRQ scores to be displayed in the above mentioned summaries will be the observed values at each visit and the absolute change from baseline at each visit.

Calculation of SGRQ score for each patient is performed on patient level based on the questionnaire manual.

Change from baseline is defined as post baseline – baseline value, assuming that both time points are non missing.

Baseline value: SGRQ following to ICF signature, see [Table 6.7:1](#).

Post baseline value: Any SGRQ score after the baseline visit.

For the statistical inference regarding the SGRQ Total score and the corresponding sub domains, mixed models for repeated measurements model (MMRM) assuming random missingness will be fit. The dependent variable will be the SGRQ (Total score or the corresponding subdomains) at each visit. Visit, GAPBSL stage, FVCBSL (cut off  $\leq 70\%$ ), DLCOBSL (cut off  $< 40\%$ ) and number of comorbidities (as dictated by the medical history page) will be entered as fixed factors, baseline score by visit as interaction term.

Patients will be fitted at random and an unstructured correlation matrix will be used, allowing adjustment for correlations between study visits within the study patients. The Kenward-Roger degrees of freedom approximation will be used in the model (ddfm=kr). In case of no convergence, the following steps will be considered:

- The value used in the model as tolerance in checking singularity should be changed to 10-10 (the default value is 10-12).
- Increase the number of convergence iterations to 200 (default is 100 iterations).
- Apply scoring algorithm. Request to use the Fisher scoring algorithm up to the 4th iteration. The default is 1.

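### An SGRQ taken at the visit where stopping nintedanib is recorded may fall weeks to months after the last dose, and the visible SAP pools it unflagged into an endpoint defined for patients under treatment.

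*Protocol*

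**What the plan says.** Protocol 9.3.2.1 states the primary endpoint as the mean SGRQ change "of patients under treatment with nintedanib, as assessed by the changes in SGRQ score at time-points of 3, 6, 9 and 12 months". Section 9.1 has observation "ending at the earliest of treatment discontinuation, withdrawal of consent" or one of several other events.

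For a patient who stops permanently, sections 9.1, 9.2.3 and 9.2.4 make the visit at which the stop is recorded the last one; in 9.2.4, "the visit that discontinuation is recorded will be considered as their final, end of study visit". Section 9.3.3 and Table 1 have the SGRQ, mMRC, cough VAS and GAD-7 completed at that final visit. The Table 1 footnote describes the early final visit differently: "or the visit performed at the time of a patient's discontinuation or withdrawal from the study". The Table 2 column heading places it after discontinuation.

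Section 9.2.4 also says that "the date of the last dose of study medication should be recorded", so the dates needed to tell on-drug from off-drug scores will exist.

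SAP 7.4.1 defines: "Post baseline value: Any SGRQ score after the baseline visit". SAP 6.7 assigns a record to a visit by the day of assessment alone, and SAP 6.3 makes the Treated Set the primary population. SAP 6.3 also plans a supportive Per Protocol Set (PPS) of completers without major deviations. It is for the primary endpoint only, and only if the two sets differ by no more than 20% in patient numbers. Deviation D3 in SAP Table 6.2:1 excludes from the PPS patients whose nintedanib was not taken or was interrupted for a 28-day period.

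**The concern.** The endpoint names a treatment condition that the analysis does not apply. Follow-up visits are about three months apart, so a patient can stop between two visits and complete the next SGRQ well into the off-drug period. That score then joins the mean for its visit on the same footing as scores from patients still taking the drug.

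The SGRQ can respond to treatment status. Part 1 asks about the past 4 weeks. Part 2 asks about the present, and its Section 5 asks about side effects and interference from medication and is skipped by patients on none.

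What is at stake is the meaning of the result. Each patient who stops can contribute one post-stop score and then nothing more. The planned estimate is therefore neither an on-treatment mean nor a mean over all patients regardless of stopping. The cough, mMRC, GAD-7 and LTOT results share the ambiguity.

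**Working it through.** **1. The plan's own precision.** Protocol Table 3 uses N = 200 and SD 16 to 22. Width = 2 × 1.96 × SD/√200.

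| SD | Computed width | Table 3 | Half-width |
|---|---|---|---|
| 16 | 4.43 | 4.4 | 2.2 |
| 18 | 4.99 | 5.0 | 2.5 |
| 20 | 5.54 | 5.5 | 2.8 |
| 22 | 6.10 | 6.1 | 3.0 |

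The table reproduces. The yardstick is a half-width of 2.2 to 3.0 points.

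**2. Possible lag from last dose to final SGRQ.** Target days in SAP Table 6.7:1 are 1, 92, 183, 275 and 366.

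- Planned spacing: 183 − 92 = 91 days at most. If stopping is uniform between visits (assumption), the mean is 91/2 = about 46 days.
- Example: last dose on day 100, next visit on day 183, lag 183 − 100 = 83 days. Day 183 lies in the 143–213 window, so the score counts as month 6.
- One visit 30 days early and the next 30 days late: (183 + 30) − (92 − 30) = 213 − 62 = 151 days.

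These are limits set by the schedule. They are not observed or typical values.

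**3. Do such scores reach the analysis?** Taking the general window column (52–132, 143–213, 235–315, 326–406), the windows cover 81 + 71 + 81 + 41 = 274 of the 365 days from day 2 to day 366, or 75%. Most final scores would map to a visit. Those in the gaps would not.

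**4. Share of records, upper bound.** Protocol 9.5 gives 240 enrolled, 200 evaluable and 17–20% dropout. That is 240 − 200 = 40, up to 0.20 × 240 = 48 patients. Assume that all stop the drug, all return for one off-drug SGRQ, and the stops are spread evenly over four intervals: 10 to 12 records per visit. The share runs from 10/240 = 4.2% (month 3) to 12/204 = 5.9% (month 12), so about 5%.

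**5. Shift in a visit mean.** Shift = share × difference between off-drug and on-drug scores. The documents give no such difference; assume 5 to 15 points. At 5%: 0.05 × 5 = 0.25 to 0.05 × 15 = 0.75. Across the full range of shares: 0.042 × 5 = 0.21 to 0.059 × 15 = 0.89.

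**6. Allowing for a 28-day cut-off.** With uniform stopping over 91 days, 28/91 = 31% of these scores fall within 28 days of the last dose. The flagged number then drops to about 0.69 × 10 = 7 to 0.69 × 12 = 8 per visit.

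**7. Will the PPS be run?** Non-completers alone take 17–20% out of the Treated Set. At 17% the room left for every other deviation is 48 − 41 = 7 patients; at 20% there is none. If the difference is measured against the PPS, 40/200 is already 20%.

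**The case against.** The documents do not support several stronger readings that a reader might infer.

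- **That final visits often come long after the last dose.** No lag or frequency is given. The Table 1 footnote describes a visit at the time of discontinuation, and a stop decided by the physician may be made at the visit itself. Only the possibility follows from the schedule.
- **That the SAP classes these scores as on-treatment.** It gives them no label; it pools in-window scores without regard to status.
- **That the SAP has no off-drug criterion at all.** Deviation D3 and the completers-only PPS remove such patients from a supportive analysis. This stands as a partial safeguard. It is limited to the primary endpoint, removes whole patients including their valid on-drug scores, and may not be run (step 7).
- **That the whole questionnaire looks back over off-drug weeks.** Only Part 1 has a 4-week recall.
- **That 9.1 contradicts 9.2.4.** Section 9.1 itself contains both the end of observation at discontinuation and the recording-visit rule. The inconsistency lies between 9.2.4, the Table 1 footnote and the Table 2 heading.
- **That 0.25 to 0.75 points is an expected bias.** It is closer to a ceiling for the assumed difference. Planned dropout includes withdrawn consent and loss to follow-up, deaths also end observation, and many of these patients would give no final SGRQ.

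Two further objections carry weight. The SAP contents list has blacked-out entries between 6.3 and 6.5 and directly after 7.4.1, so a relevant sensitivity analysis cannot be ruled out. And a discontinuer's last score may be the only late information on that patient. Deleting it could make the mean look better and remove data that support the missing-at-random model. That argues against replacing the planned analysis, but not against adding a flagged one beside it.

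**Conclusion.** The point holds as a matter of what the primary result means. The endpoint is worded for patients under treatment. The schedule allows a final SGRQ up to about 91 days after the last dose (about 151 at the window extremes), and the visible Treated Set analysis neither excludes nor marks it, although the last-dose date is collected. The PPS does not close the gap reliably.

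The numerical effect is probably small: about 5% of records per visit as an upper bound, moving the mean by 0.25 to 0.75 points if off-drug scores differ by 5 to 15 points, against a half-width of 2.2 to 3.0. That rests on 40 to 48 discontinuers, all returning for one off-drug score and evenly spread, and on a difference that the documents do not give. It is no ground for expecting a changed conclusion in a study that Protocol 9.7.1 calls exploratory and descriptive. It is a cheap improvement worth making, with the caveat that redacted SAP sections could not be checked.

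**What to change.** 1. **Protocol.** Reconcile section 9.2.4, the Table 1 footnote and the Table 2 column heading on when the final visit of a patient who stops takes place, so that all sites follow one description.
2. **SAP 7.4.1 and 7.5.2.** Derive days from last dose to each questionnaire. Flag records beyond a pre-specified lag. For example, 28 days would be in line with deviation D3, purely as an analysis cut-off and not as a treatment rule.
3. **Reporting.** Keep the all-records MMRM in the Treated Set. Beside it, report the estimate without flagged records as the under-treatment result, with the number of flagged records at each visit. Do the same for the secondary endpoints.
4. **Interpretation.** Say in the SAP what each estimate describes. With flagged scores set to missing, an MMRM under missing at random in effect carries discontinuers on as if still treated, whereas the observed summaries describe only those still on drug.

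The cost is SAP wording, one derived variable and one extra model run per scale, on dates already collected. The under-treatment estimate will have fewer records and may look more favourable because discontinuers' last scores are removed, so the two estimates must always be shown together.

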### 6.3 SUBJECT SETS ANALYSED

The following sets will be used for the purpose of the statistical analysis of the current trial:

Treated Set (TS): all subjects entered the trial received at least once Nintedanib during the trial. TS will be used for safety analysis. Any analysis on primary, secondary and safety endpoints will be performed in TS.

Per Protocol Set (PPS): all subjects who have completed the trial with no major protocol deviations. PPS will be used only as supportive to the TS and only in the analysis of the primary endpoint providing that the TS does not differ more than 20% from the PPS in the number of patients.

Table 6.3:1 Subject Sets Analysed

Class of endpoint	Subject Sets	
	TS	PPS
Primary endpoints	primary analysis	secondary analysis
Secondary endpoints	X	
Safety endpoints	X	
Demographic/baseline endpoints	X	

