## **6.6 HANDLING OF MISSING DATA AND OUTLIERS**

No imputation technique to fill in any missing values will be employed. Accordingly, the Last Observation Carried Forward technique or any other multiple imputation will not be applied.

Missing values will be differentiated from negative answers. Summary statistics will be performed only on subjects with available information (unknown data will not account in the total population for each specific variable).

For missing or incomplete AE dates or drug administration dates, or other significant dates, the BI internal procedures and guidelines (2) will be employed.

In case implausible data remain in the database once locked, then: for tables that are provided for endpoints with a large amount of implausible data, median, quartiles and percentiles should be preferred to mean, standard deviation, minimum and maximum.

Correction of implausible data on an individual subject case is not permitted.

In order to account for the missing values of the primary and secondary continuous endpoints, an MMRM model will be employed based on the assumption that values as missing at random.

Note: Due to incorrect translation in the Greek language of question 17 of the SGRQ instrument this specific question has been set to missing in all patients prior to the approval receipt date as mentioned in [Table 9.1:1](#). The corrected version to be considered is the one used after the approval receipt date. No further action is to be performed to impute this data for the primary analysis of the primary

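### SGRQ collection stops at nintedanib discontinuation or death, and no readable analysis tests the missing-at-random assumption on which the month-12 change then depends

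*Protocol*

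**What the plan says.** **Follow-up.** Protocol 9.1, 9.2.3 and 9.2.4 end study follow-up at permanent discontinuation of nintedanib for any reason. Such patients "patients will be considered as prematurely/early discontinued and will not be further followed up in the scope of the study". Protocol 9.1 lists the events that close observation, ending with "12-month observation period completion, death or any other discontinuation criterion is met".

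**Last visit.** The footnote to Table 1 (Protocol 9.3.3) defines the final visit as month 12 or "the visit performed at the time of a patient's discontinuation or withdrawal from the study". Tables 1 and 2 mark the SGRQ for that visit, so a score at stopping is scheduled. None is scheduled afterwards.

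**Endpoint.** Protocol 9.3.2.1 defines it as the mean SGRQ change "of patients under treatment with nintedanib, as assessed by the changes in SGRQ score at time-points of 3, 6, 9 and 12 months".

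**Missing data.** SAP 6.6 states that "an MMRM model will be employed based on the assumption that values as missing at random", and that "the Last Observation Carried Forward technique or any other multiple imputation will not be applied". Protocol 9.7.1 also rules out imputation. SAP 7.4.1 gives the model.

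**Other readable analyses.** There are observed-case summaries by visit, and a supportive Per Protocol Set (PPS) defined as "all subjects who have completed the trial with no major protocol deviations". The PPS is used only if it differs from the Treated Set by no more than 20% in patient number. SAP 7.8.5 reports deaths in a table and a Kaplan-Meier curve, with no link to the SGRQ.

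**The concern.** The study's own rule creates much of the missing SGRQ data, and it does so when patients stop treatment or die. An MMRM under MAR gives these patients, in effect, the later course of similar patients who stayed. The month-12 estimate therefore describes the mean change as if everyone had remained alive and on nintedanib. Nothing in the readable text says so. The stated aim, HRQoL over 52 weeks in patients treated in practice, can be read more broadly.

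The other readable analyses do not test MAR. The PPS keeps completers only, so it is more selected than the main set. Observed-case means condition on having stayed. Protocol 9.9 does not name informative dropout.

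At stake is how a 52-week change near zero would be read. It could mean that HRQoL was stable, or that patients who deteriorated had left.

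**Working it through.** **Inputs from the documents**
- Planned loss 17-20%, with 240 enrolled and 200 evaluable, and discontinuation of nintedanib given as the reason (Protocol 9.5).
- SD of the week-52 SGRQ change 16 to 22; mean changes 2 to 5 (Protocol 9.5, Table 3).
- A difference of 4 points, which applies to COPD; none is established for IPF (Protocol 7.6.1).

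**Input not in the documents.** The shift is the number of points by which leavers are worse at month 12 than MAR predicts. It is an assumption, shown from 0 to 20.

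**Step 1: reproduce Table 3.** Half-width = 1.96 × SD / √200.
- SD 16: 1.96 × 16 / 14.14 = 2.22, full width 4.43 (printed 4.4).
- SD 22: 1.96 × 22 / 14.14 = 3.05, full width 6.10 (printed 6.1).

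All 16 rows agree to within 0.1. Enrolment: 200 / 0.83 = 241, close to 240. At 20% loss, 240 × 0.80 = 192 evaluable, with half-widths 2.26 and 3.11.

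**Step 2: size of the understatement.** Understatement = fraction lost × shift.

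| Shift (assumed) | 17% lost | 20% lost |
|---|---|---|
| 0 | 0 | 0 |
| 4 | 0.68 | 0.80 |
| 10 | 1.70 | 2.00 |
| 20 | 3.40 | 4.00 |

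**Step 3: compare with the planned precision.** The understatement equals the half-width at these shifts:
- SD 16: 2.22 / 0.20 = 11.1 to 2.22 / 0.17 = about 13.
- SD 22: 3.05 / 0.20 = 15.2 to 3.05 / 0.17 = 17.9.

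It reaches 4 points at 4 / 0.20 = 20 to 4 / 0.17 = 23.5.

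**Step 4: effect on one planned row.** Take a reported change of 2 with SD 16, for which the lower limit is 2 - 2.22 = -0.22. Treating the share lost as fixed, a shift of 0.22 / 0.20 = 1.1 to 0.22 / 0.17 = 1.3 brings that limit to zero. A shift of 2 / 0.20 = 10 to 2 / 0.17 = 11.8 brings the mean to 4.

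**Step 5: check by simulation.** The set-up was 240 patients, SD 16, monotone dropout of about 17% driven by the last observed SGRQ, and sequential-regression maximum likelihood, which is equivalent to an unstructured MMRM.
- Shift 0: MMRM bias 0.0; the observed-case mean is about 1.0 point too favourable.
- Shifts 5, 10 and 20: the MMRM is too favourable by 0.8, 1.7 and 3.4 points, as the formula predicts.

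**Step 6: does the discontinuation score reach the model?** SAP Table 6.7:1 leaves days 2-51, 133-142, 214-234 and 316-325 in no window: 50 + 10 + 21 + 10 = 91 of the 365 days from day 2 to day 366, or 25%. An SGRQ taken at stopping on one of those days has no analysis visit.

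**The case against.** The strongest objection is to the inference a reader might draw, that the 52-week change will look too favourable. The documents do not support that. Bias needs leavers to be worse than MAR predicts, and no figure for leavers is given. If dropout depends only on observed scores, the MMRM is unbiased (step 5), and the scheduled discontinuation-visit SGRQ helps it to use those scores. Leavers also include patients who withdraw consent, are lost to follow-up or join another trial. For stopping through intolerance the sign is unclear: the SGRQ has items on medication side effects, and patients on no medication skip that section. All of this stands, and it limits the claim to a possibility.

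A reader might also infer that the SAP contains nothing further. The redacted contents entry after 7.4.1 prevents that conclusion. The SAP 6.6 note on question 17 limits its no-imputation statement to the primary analysis, which leaves room for others. Nor does the bar on imputation rule out a check: step 2 is itself a shift analysis and imputes nothing.

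The endpoint wording, under treatment, suggests that an on-treatment mean was intended. This stands in part. A month-12 MMRM mean is not a while-on-treatment summary, however; it projects leavers to month 12 as if still treated. The documents do not choose between the two.

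Finally, the study is descriptive and tests no hypothesis. That is so, but SAP 7 and 7.4.1 plan 95% confidence intervals, and these do not include this uncertainty.

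**Conclusion.** The point holds in conditional form. Follow-up ends at discontinuation or death, a loss of 17-20% is planned, and the readable analysis relies on MAR without testing it. The month-12 change may look too favourable, by 0.7-0.8 points at a shift of 4 and 1.7-2.0 at a shift of 10. Both shifts are assumed, and both results lie below the smallest planned half-width of 2.2. They still matter against changes of 2-5 points: at the upper end a true worsening of 2 would be reported as about zero.

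The direction is plausible. Protocol 7.1 describes progressive disease with poor prognosis, and 7.4 cites a 14.2% one-year incidence of acute exacerbation. Visits are three months apart, so abrupt decline can fall between scores. Plausible is as far as the documents go.

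The calculation applies one shift to all losses. For patients who die it describes a hypothetical score, which is why deaths need separate treatment. This is an inexpensive improvement to the plan and not the correction of an invalid analysis.

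**What to change.** 1. **SAP 7.4.1, label.** State that the MMRM estimates the mean change as if all patients had stayed alive and on nintedanib. Show the numbers discontinued and died beside each visit.
2. **SAP 7.4.1, sensitivity analysis.** Add one delta-adjusted analysis of the month-12 SGRQ total change, with scores after discontinuation made worse by 0 to about 20 points. Report the shift at which the 95% CI first excludes zero and the shift at which the mean change reaches 4 points, as descriptive marks, since the study defines no conclusion to overturn. Handle deaths separately and do not give them imputed scores under the same shift. If multiple imputation is used, allow it as an exception in both SAP 6.6 and Protocol 9.7.1.
3. **SAP 6.7.** Add a rule that keeps discontinuation-visit SGRQ scores in the model when they fall in a gap of Table 6.7:1, for example by assigning them to the nearest analysis visit without a score.
4. **Protocol 9.9.** Name informative dropout as a limitation.

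The cost is some programming and one extra table, with no new data or visits. The downside for the sponsor is a less favourable reported range. If the redacted SAP text already contains such an analysis, item 2 reduces to checking it against this description.
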